The participants who choose to consent and enroll in the study will then complete either the EEsAI (age 18 -60) or the PedsQL (age 6-17), both validated questionnaires that assess patient symptoms of EoE. Additionally, all study participants will have their initial Esophagogastroduodenoscopy (EGD) images evaluated via Endoscopic Reference Score (ERFS). This scoring system is a validated tool that has demonstrated moderate to good inter-observer variability. The PI for this protocol will be the physician who assigns a score to pre and post intervention images, in order to limit variations between graders. The 6-8 esophageal biopsies taken at initial EGD will be evaluated by pathology per routine protocol to provide primary diagnosis. Again to limit variation, there are two pathologists serving on this protocol as AIs that will be evaluating the specimens obtained during this research period. Each set of biopsies will then be evaluated by 1 of these 2 pathologists to record the number of eosinophils per high power field (HPF). Immunohistochemical staining on these biopsies for eotaxin-3 will be performed on the Ventana Ultra platform after stain optimization based on previously described protocols. Staining will be evaluated by 1 of 2 pathologists for intensity and percentage of cells staining (Allred scoring system). [name] will be performing research as a credentialed provider at WRNMMC Department of Pathology, although he is assigned to Joint Pathology Center.

The participants will be randomized into 2 groups: 1) omeprazole + swallowed fluticasone and 2) placebo + swallowed fluticasone. The placebo will replicate oral omeprazole. The study participants will be randomly assigned with concealment of allocation to one of the treatment groups, with each group having an equal number of participants (1:1 ratio).

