The sample size was estimated for the primary outcome utilizing a two-sided likelihood ratio chi-square test of two independent proportions. The following parameters were used in this calculation: alpha of 0.05 and a power of 0.80. A response rate in the control group of fluticasone alone (reference proportion) was estimated to be 50% based on the study Konikoff et al.⁶ The estimated response rate for the treatment arms are based on clinical experience as was estimated to be in the range of 70% to 80%. This graph demonstrates that the sample size estimation may vary anywhere from 78 to 180 subjects. We plan to enroll approximately 100 patients.

11.3 Total number of subjects requested (including records and specimens):

100

11.4 If you are recruiting by study arm, please identify the arms of the study and how many subjects will be enrolled in each arm

50 subjects in each arm - one arm will be fluticasone and placebo, one arm will be fluticasone and omeprazole.

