11.5 Please provide a justification for your sample size

The sample size was estimated for the primary outcome utilizing a two-sided likelihood ratio chi-square test of two independent proportions. The following parameters were used in this calculation: alpha of 0.05 and a power of 0.8. A response rate in the control group of fluticasone alone (reference proportion) was estimated to be 50% based on the study Konikoff et al (6). The estimated response rate for the treatment arms are based on clinical experience as was estimated to be in the range of 70% to 80%. This graph demonstrates that the sample size estimation may vary anywhere from 78 to 180 subjects. We plan to enroll approximately 100 patients.

11.6 Data Analysis Plan:

Outcome variables are listed in the following table. All continuous data will be evaluated for normality of the data using both univariate methods, visual inspection, and the Kolmogorov Smirnov test. Differences in continuous data that is normally distributed will be tested using parametric tests and for data that is not normally distributed a nonparametric test. Likert scale data will be transformed into numerical data and evaluated as continuous variables.

Outcome variables	Variable Type	Statistical Test
Primary Outcome Tissue esophageal eosinophils < 15/ hpf	Binary categorical	Two-sided likelihood ratio chi-square test of two independent proportions

Change in EEsAI	Likert scale - continuous	Normally distributed data: t-test Non-normally distributed data: Mann-Whitney U
Change in PedsQL	Likert scale - continuous	Normally distributed data: t-test Non-normally distributed data: Mann-Whitney U
Change in EREFS	Continuous	Normally distributed data: t-test Non-normally distributed data: Mann-Whitney U
Change in eosinophils per hpf	Continuous	Normally distributed data: t-test Non-normally distributed data: Mann-Whitney U
Change in tissue eotaxin level	Continuous	Normally distributed data: t-test Non-normally distributed data: Mann-Whitney U

Although all outcomes will be evaluated and reported using pooled data, a priori planned subgroup analysis will include a stratification of the analysis and results based on adult and pediatric subject groups.

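### The age-group analysis gives separate adult and pediatric results with no treatment-by-age comparison, so it cannot show whether the effect differs by age and can easily suggest that it does

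*Combined protocol and SAP*

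**What the plan says.** Section 11.6 (Data Analysis Plan) reports every outcome on pooled data and then states that "a priori planned subgroup analysis will include a stratification of the analysis and results based on adult and pediatric subject groups". The tests it lists are all two-sample comparisons of the arms. The primary outcome, fewer than 15 eosinophils/hpf, uses a "two-sided likelihood ratio chi-square test of two independent proportions". The change scores use a t-test or Mann-Whitney U test.

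No treatment-by-age interaction, subgroup confidence interval, subgroup multiplicity rule or rule for reading the age-group results appears anywhere. The form prompt in section 11.1 asks for subgroup analyses and their methods. The answer points to 11.4, which gives only the arm sizes: "50 subjects in each arm". Section 2.3 of the abstract describes block randomization and does not mention stratifying it by age. No adult/pediatric split is stated.

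Section 10.1 gives EEsAI to adults and PedsQL to ages 6-17, and sets the drug regimens separately for the two age groups.

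**The concern.** The natural reason to split results by age is to ask whether omeprazole adds the same benefit in adults and in children. Two separate tests do not answer that. A significant result in one group and a non-significant one in the other is compatible with identical effects, because each test has roughly half the data or less. The relevant quantity is the difference between the two treatment effects, and the plan does not ask for it.

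With 100 subjects, discordant p-values would be common even if age made no difference. The trial report could then suggest benefit in only one age group. Because age group also fixes the regimen, readers could take the same pattern as evidence about the regimens.

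**Working it through.** **Inputs from the documents.** Sections 11.2 and 11.5: two-sided alpha 0.05, power 0.80, control response 50%, treated response 70-80%. Section 11.4: 50 per arm.

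**Assumptions.** Adult/pediatric split: even (25 per arm in each age group), with 35/15 and 40/10 per arm as alternatives. Arms are balanced within age. Control and treated response rates are the same in both age groups.

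**Step 1: the plan's own sample size.** The plan says "the sample size estimation may vary anywhere from 78 to 180 subjects". The pooled-variance formula per arm, with p̄ the mean of p1 and p2, is

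n = [1.96·√(2p̄(1−p̄)) + 0.8416·√(p1(1−p1) + p2(1−p2))]² / (p2−p1)²

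- 50% vs 80%: (1.322 + 0.539)² / 0.09 = 38.5, so 39 per arm and 78 in total. This matches.
- 50% vs 70%: (1.358 + 0.571)² / 0.04 = 93.0, so 93 per arm and 186 in total. The unpooled formula gives 182, and 90 per arm has 78.7% power. The stated 180 is therefore reproduced approximately.

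**Step 2: power within an age group.** For each pair of binomial counts compute G = 2·Σ O·ln(O/E), where O and E are observed and expected cell counts. Add up the probabilities of all pairs with G > 3.841.

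**Step 3: agreement of the two tests.** The age groups are independent. With powers b1 and b2:

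P(exactly one significant) = b1(1−b2) + b2(1−b1)

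Example, 25/25, 50% vs 75%: 2 × 0.479 × 0.521 = 0.499. Example, 35/15, 50% vs 75%: 0.608 × 0.707 + 0.293 × 0.392 = 0.545.

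| Per arm, by age group | Treated response | Power in each group | Exactly one | Both | Neither |
|---|---|---|---|---|---|
| 25/25 | 70% | 33%, 33% | 44.5% | 11% | 44.3% |
| 25/25 | 75% | 48%, 48% | 50% | 23% | 27% |
| 25/25 | 80% | 64%, 64% | 46% | 41% | 13% |
| 35/15 | 70% | 42%, 20% | 44.9% | 8% | 47.0% |
| 35/15 | 75% | 61%, 29% | 54% | 18% | 28% |
| 35/15 | 80% | 78%, 42% | 55% | 33% | 13% |
| 40/10 | 70% | 46%, 16% | 47% | 8% | 45% |
| 40/10 | 75% | 65%, 24% | 58% | 15% | 26% |
| 40/10 | 80% | 83%, 33% | 61% | 28% | 12% |

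**Step 4: sensitivity.** The normal approximation gives, for exactly one at 70%, 75% and 80%:

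- even split: 42%, 49%, 48%
- even split with 20% dropout: 37%, 47%, 50%
- 80:20 split: 46%, 58%, 64%

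The overall range is 37-64%.

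**Step 5: does a positive pooled result protect against this?** Among simulated trials with a significant pooled test (even split), exactly one age group is significant in 65%, 59% and 49%.

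**Step 6: an interaction test on the same scenarios.** This is a Wald test on the difference in log odds ratios, with 0.5 added to each cell, by simulation.

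| Per arm, by age group | False signal, equal effects (70/75/80%) | Power, effect in one group only (70/75/80%) |
|---|---|---|
| 25/25 | 4.7 / 4.3 / 3.9% | 18 / 26 / 36% |
| 35/15 | 4.1 / 3.8 / 3.5% | 15 / 23 / 33% |
| 40/10 | 3.4 / 3.2 / 3.1% | 13 / 19 / 27% |

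At the unequal splits, the power column puts the effect in the larger age group.

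**The case against.** The strongest reply is that the plan commits to no wrong inference. The main analysis is pooled, and the hypothesis and sample size ignore age. No rule declares efficacy within an age group, and nothing says the two p-values will be compared. The 44-50% is the chance of discordant p-values, which is not the same event as a false conclusion or as a false-positive interaction. All of that stands. It limits the harm to interpretation of a secondary analysis. It does not supply the missing comparison, and step 5 shows that a positive pooled result would often come with discordant age results.

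The wording could also mean one age-stratified analysis or a stratified presentation. Separate results are the likelier reading, because the sentence calls this a subgroup analysis, splits the results by age and contrasts them with pooled data. On either reading, no comparison of effects between ages is named.

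Three stronger readings are not supported:

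- A reader might infer that discordance is always the most likely outcome when effects are equal. At 70% response it ties with neither being significant at 25/25 (44.5% vs 44.3%) and is less likely at 35/15 (44.9% vs 47.0%).
- A reader might infer that the likelihood ratio test generally exceeds 5% in groups this small. At 50% response its exact size is 4.6% at 15 and at 35 per arm, 5.2% at 10 and 6.5% at 25. It does rise to 7.7-8.7% at 10 per arm with 70-80% response. The excess is not general, and it is a separate matter that an interaction test would not address.
- A reader might infer a flat 50% chance that the trial concludes omeprazole works in only one age group. That figure needs an even split and 75% response, neither fixed by the documents, and an efficacy rule by age that the plan does not contain.

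**Conclusion.** The point holds as a weakness in a secondary analysis and should be corrected. The planned age-group results cannot show whether the effect differs by age. With identical effects at the plan's own response rates, exactly one age group would be significant in about 44-50% of trials at an even split and 45-61% at the uneven splits tried. These figures apply to the binary primary outcome, with success meaning p < 0.05 within the age group. They rest on an assumed split and on arms balanced within age. The primary test, its error rate and its power are untouched.

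**What to change.** In section 11.6, for the outcomes measured in both ages (response below 15/hpf, change in eosinophils, EREFS and eotaxin-3):

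- report the treatment effect with a 95% CI in each age group;
- add a treatment-by-age-group interaction estimate with its CI and test, naming the scale (for the binary outcome, for example, the log odds ratio);
- label the analysis exploratory, and state that no age-specific efficacy conclusion will be drawn from within-group p-values;
- state that age group and dose regimen cannot be separated in this design.

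Exempt EEsAI and PedsQL. Each is measured in one age group only, so a within-age comparison is the only one available.

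The cost is a few lines of text and one model term per outcome. The downside to state in the plan is low power: about 18-36% at an even split if the effect exists in only one age group, and less at uneven splits. A non-significant interaction must not be reported as evidence of equal effects.

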12.0 Participant Information

12.1 Subject Population:

-Male and female military health care beneficiaries age 6 to 60 years presenting with a new diagnosis of eosinophilic esophagitis.
 -There will be no exclusion based on race or gender. Children will be included in this study given the fact that a significant number of patients diagnosed with EoE are identified during childhood and adolescence. The primary benefit for children enrolled in this study would be that they will be more closely tracked by a consistent nurse coordinator or GI provider to prevent loss of follow up and to ensure adherence to medications and treatment. The primary benefit for adults enrolled in this study would be more closely monitored care from a consistent nurse coordinator or GI provider to prevent loss of follow up and to ensure adherence to medications and treatment.

12.2 Age Range:

Check all the boxes that apply. If the age range of potential subjects (specimens, records) does not match the range(s) selected, please specify in the text box.

- 0-17
- 18-24
- 25-34
- 35-44
- 45-54
- 55-64
- 65-74
- 75+

12.3 Gender:

- Male

- Female
- Other

12.4 Special categories, check all that apply

- Minors /Children
- Students
- Employees - Civilian
- Employees - Contractor
- Resident/trainee
- Cadets /Midshipmen
- Active Duty Military Personnel
- Wounded Warriors
- Economically Disadvantaged Persons
- Educationally Disadvantaged Persons
- Physically Challenged (Physical challenges include visual and/or auditory impairment)
- Persons with Impaired Decisional Capacity
- Prisoners
- Pregnant Women, Fetuses, and Neonates
- Non-English Speakers
- International Research involving Foreign Nationals - Headquarters Review is necessary

You must also consider the requirements of 45 CFR 46 Subpart D and DoDI 3216.02, Enclosure 3, paragraph 7.d.

You must also consider the requirements of DoDI 3216.02, Enclosure 3, paragraph 7.e.

12.5 Inclusion Criteria:

Order Number	Criteria
1	DEERS eligible
2	At least 6 years of age and < 60 years of age
3	presenting with initial diagnosis of EoE (symptoms may include dysphagia, abdominal pain, vomiting, gastroesophageal reflux, weight loss, feeding aversion)
4	require EGD as part of clinical evaluation

12.6 Exclusion Criteria:

Order Number	Criteria
1	age < 6 years or > or = 60 years
1	any concurrent or ongoing treatment with oral steroids.

2	any known diagnosis of a gastrointestinal inflammatory condition other than EoE. These conditions include ulcerative colitis, crohn's disease, celiac disease, and eosinophilic colitis.
3	pregnant women (due to increased risks for injury to the fetus during sedation/anesthesia screening for pregnancy is part of routine standard of care prior to procedures)
4	refusal to undergo endoscopy

13.0

Recruitment and Consent

13.1 Please describe the recruitment process, including how subjects will be identified and selected for the study.

Subjects will be recruited from the Adult and Pediatric Gastroenterology clinics at WRNMMC, during routine patient care appointments. Potential subjects will be identified by their primary gastroenterologist based on their clinical presentation and need for endoscopy. Once a subject is referred, they will be briefed on the study protocol by one of the investigators and given opportunities to ask any questions regarding the study. No HIPAA preparatory research will be required. If consent is provided, the subject will be enrolled in the study.

13.2 Compensation for Participation:

Study participants will not be compensated for their participation in the study.

13.3 Please describe the pre-screening process. If no pre-screening, enter Not Applicable in the text editor

Subjects will be identified through the primary Gastroenterologist in adult and pediatric gastroenterology clinics at Walter Reed National Military Medical Center. No HIPAA preparatory research provision will be required. Once a patient has been consented, the investigator will determine if the study subjects meets eligibility criteria.

13.4 Consent Process:

Are you requesting a waiver or alteration of informed consent?

Yes No

Please explain the consent process:

Once a subject has been referred, they will then meet with one of the GI nurses to schedule their EGD. At that time, an investigator will explain the study at length, answer any questions, and administer the informed consent. Subjects will be reminded that enrollment is purely voluntary and that they will receive the standard of care, regardless of whether they choose to enroll or not. The parent or guardian of children 6-17 years old will be asked to sign a consent form prior to study enrollment, and all questions will be answered. Any subjects between the ages of 8-17 years will also be provided an Assent

form to help provide additional age appropriate information regarding the study. If a subject turns 18 years old during the study time frame, he or she will need to be consented when they return for their next office visit.

13.5 DoDI 3216.02 requires an ombudsman to be present during recruitment briefings when research involves greater than minimal risk and recruitment of Service members occurs in a group setting. If applicable, you may nominate an individual to serve as the ombudsman.

- N/A
- Propose ombudsman

13.6 Withdrawal from Study Participation:

Explain the process for withdrawal and specify whether or not the subjects will be given the opportunity to withdraw their data their data/specimens in the event they wish to withdraw from the study

In the consent form, the patient's right to withdraw from study participation is covered in detail. Subjects must notify the primary investigator via phone or email and return all study medication if they decide to withdraw. By leaving the study at any time, subjects will not risk losing their right to medical care or benefits within the military treatment facility. Subjects who withdraw will be referred to their primary gastroentetologist for continued care in accordance with acceptable standards of medical treatment.

14.0 Risks and Benefits

14.1 Risks of Harm:

Identify all research-related risks of harm to which the subject will be exposed for each research procedure or intervention as a result of participation in this study. Consider the risks of breach of confidentiality, psychological, legal, social, and economic risks as well as physical risks. Do not describe risks from standard care procedures; only describe risks from procedures done for research purposes

Research participants will not be exposed to any more risks than what are experienced by non-study patients being evaluated and treated for Eosinophilic Esophagitis. All interventions are within standard of care parameters in either treatment or control arm. It should be noted that there are risks associated with the EGD procedure to include bleeding, pain, infection, and intestinal perforation. There are also risks associated with the anesthetics used. However, patients who do not participate in the study would be subject to the same frequency and risks of EGD procedures.

14.2 Measures to Minimize Risks of Harm (Precautions, safeguards):

For each research procedure or intervention, describe all measures to minimize and/or eliminate risk of harms to subjects and study personnel

Safety Monitoring Plan

Participants will have cardiorespiratory monitoring throughout the endoscopic procedures, and will undergo pre procedure and post procedure monitoring per hospital protocol. The participant will receive a standard follow up call for biopsy results from the respective clinic, as is the standard of care for all patients who receive endoscopy. In addition, study participants will receive a telephone follow up 4 weeks after starting therapy.

Safety Analysis Plan

At the 4 week phone follow up, participants will be asked about any symptoms that have started since study treatment began. If worsening symptoms, patient will be brought in for a clinic visit to further evaluate ability to continue in trial.

14.3

Confidentiality Protections (for research records, data and/or specimens):

Describe in detail the plan to maintain confidentiality of the research data, specimens, and records throughout the study and at its conclusion (e.g., destruction, long term storage, or banking). Explain the plan for securing the data (e.g., use of passwords, encryption, secure servers, firewalls, and other appropriate methods). If data will be shared electronically with other team members/collaborators outside the institution, describe the method of transmission and safeguards to maintain confidentiality. Explain whether this study may collect information that State or Federal law requires to be reported to other officials or ethically requires action, e.g., child or spouse abuse

All hard copies of data will be kept in a locked file cabinet in the office of the PI at WRNMMC. The spreadsheet with EEsAI or PedsQL scores, EREFS score, histology and demographics will not include any names of the subjects, and will only be identified by numeric code. These codes will be randomly assigned by the PI, and the subjects identity will be stored electronically on the PIs password protected computer. Each unique subject code will be determined by whether they are an adult or pediatric subject, and their general chronological order of recruitment using only odd or even numerals (ie, P-5, A-22). All codes will be alphanumeric in nature.

All data will be stored and organized on a spreadsheet table. An alpha-numeric code will be assigned to each subject who will be used to identify the subject on the spreadsheet table. The PI will assign these codes, and PI and Research Monitor will only have access to the subject identifier codes on a master list. The research file will be stored electronically on the PIs password protected computer. The master list will be destroyed 5 years after study completion. All de-identified data related to the study will be destroyed 10 years after study completion.

14.4

Potential Benefits:

Describe any real and potential benefits of the research to the subject and any potential benefits to a specific community or society

If the individuals in the research are considered experimental subjects (per 10 USC 980), and they cannot provide their own consent, the protocol must describe the intent to directly benefit all subjects

Study participants may benefit directly from participation by close evaluation and treatment with fluticasone in both treatment and control arms, which is an accepted standard medical treatment for patients with Eosinophilic Esophagitis, helping to relieve often-painful symptoms. They will also receive close follow up throughout the study period, to ensure adherence to treatment.

14.5

Privacy for Subjects:

Describe the measures to protect subject's privacy during recruitment, the consent process, and all research activities, etc.

No PHI will be removed from the covered entity by the research team in the course of the review. The PHI being used or disclosed is necessary for the research purposes. No research data, including Protected Health Information, will be sent outside of WRNMMC.

The subject's privacy will be protected by performing all study procedures in a private room; this includes obtaining consent and medical history, performing exams, and test. The only personnel that will be present will be the study investigator, study coordinator and staff, such as nurses, who will perform procedures under the direction of the study investigator. Any other persons will need explicit consent of the subject to be presented. The subject and his or her parents will be made to feel at ease by limiting the number of personnel present, and encouraging the subjects to ask question and notify the staff if he or she is uncomfortable in any way.

14.6 Incidental or Unexpected Findings:

Describe the plan to address incidental findings and unexpected findings about individuals from screening to the end of the subject's participation in the research. In cases where the subject could possibly benefit medically or otherwise from the information, state whether or not the results of screening, research participation, research tests, etc., will be shared with subjects or their primary care provider. State whether the researcher is obligated or mandated to report results to appropriate military or civilian authorities and explain the potential impact on the subject

Expected adverse events which are not serious are reported on the Continuing Review (CR) Progress Report. CR is generally performed on a 12-month cycle. More frequent Progress Reports will be provided at the discretion of the IRB.

Serious Adverse Events: The PI, within 24 hours, will report all related or possibly-related AND serious adverse events (SAE) occurring in subjects enrolled at WRNMMC. Serious adverse events will be reported even if the PI believes that the adverse events are unrelated to the protocol.

Unexpected (but not serious) adverse events occurring in subjects enrolled at WRNMMC which, in the opinion of the PI, are possibly related to participation AND places subjects or others at a greater risk of harm that was previously known or recognized in the protocol will be reported by the PI within 24 hours of discovery by email or phone to the IRB and the Research Monitor. A follow-up written report within 5 business days to the IRB and the Research Monitor is required.

Unanticipated problems involving risks to subjects or others (UPIRTSOs) will be reported to the IRB and Research Monitor via email or telephone within 24 hours of discovery and a written follow up report within 5 business days.

